# 4.2. Intervention.

All procedures will be conducted as part of standard of care. In the Pharmacist Care group, each e-visit message requesting Paxlovid will be assigned to a pharmacist on the regional team. Pharmacists will review requests using a standard protocol. They will call patients via telephone to elicit additional information where needed, file Paxlovid prescriptions when appropriate, and arrange home delivery when requested.

The protocol for pharmacists has a list of common potential drug-drug interactions and provides guidance for how these should be handled. Drug-drug interactions are documented by pharmacists using a smartphrase in Epic, the electronic health record (EHR). Some DDIs may lead to changes in medications while a patient is taking Paxlovid.

In the AFM Pool Care group, each e-visit message requesting Paxlovid will be assigned to a pool of AFM physicians based at the medical centers in a given service area. Physicians will review requests using the existing standard regional protocol (as well as any existing medical center-level protocols). The regional Paxlovid E-visit User Guide illustrates how to use SmartSets to document the plan and respond to patients with the outcome (eligible, not eligible, or further discussion needed). Following this protocol, physicians call patients via telephone to elicit additional information where needed, file Paxlovid prescriptions when appropriate, and arrange home delivery when requested.

4.3. Randomization. In each of the participating service areas, facilities have been assigned at random to either the Pharmacist Care or AFM Pool Care group. We used covariate-constrained randomization, a method to prevent imbalances on important variables that may be associated with the outcomes. We conducted preliminary analyses to characterize facilities with regard to population size, socioeconomic status (using the Neighborhood Deprivation Index), race, ethnicity, and COVID-19 incidence in the service area since the start of the pandemic. We have chosen these variables for use in the restricted randomization given the expected association with study outcomes, along with the expected level of between facility variability which would increase the likelihood of between-arm imbalance. We also stratify randomization on service area for within-area balance on number of facilities assigned to the Pharmacist Care and AFM Care groups.

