#### 4.4. Main outcomes and measures

#### 4.4.1. Outcomes

The primary outcome will be measured only among patients who have common potential drugdrug interactions (DDIs) based on a pre-specified list of medications. The outcome will be whether the patient received counseling for any valid potential DDI. For patients with more than one DDI, the outcome will counted as present if they received counseling for any of their potential DDIs.

Secondary outcomes will be:

- a. % of all patients who were prescribed Paxlovid (based on orders)
- b. Hours from the e-visit request to the prescription order being placed, among patients who were prescribed Paxlovid
- c. Clinician minutes per message handled. This will be analyzed using EPIC access log data. We will link each e-visit for Paxlovid with the relevant secure messages and/or

telephone encounters, including follow-ups that occurred before the initial request was resolved. Clinicians include pharmacists and physicians.

- d. Estimated personnel cost per Paxlovid message handled. The estimated cost per message handled will be calculated by multiplying the number of minutes spent per message by the standard wage rate for a pharmacist or AFM in Northern California.
- e. Patient satisfaction with care

Exploratory outcomes will be:

- a. Number of Paxlovid e-visits handled by the regional pharmacy team, per week
- b. % of messages fully handled by the initial clinician (pharmacist or AFM) (based on review of visits)
- c. % of cases handled by pharmacists that required a physician consultation (based on review of visits)
- d. Pharmacist satisfaction with the process of care [Note: Deleted "AFM satisfaction" as a measure because there was not a logical group of AFMs to survey, nor logical questions to ask them.]
- e. % of all patients who obtained Paxlovid (based on fills)
- f. Days from request to receipt of medication among patients prescribed Paxlovid
- g. % of patients with common potential DDIs who were prescribed Paxlovid
- h. If feasible based on ICD-9 codes: Incidence of drug reactions due to Paxlovid DDIs within 10 days after a Paxlovid prescription

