The pharmacist and physician surveys have been designed to require no more than 3 to 5 minutes to complete. These surveys will be fielded via Outlook email using a Teams form, as well as on paper via interoffice mail. A small gift to thank pharmacists and physicians for considering participation will be included in the mailing. Responses will be treated as confidential and data will be aggregated, with no individual identifiers associated with data presented in reports.

Data collected from both pharmacists AFMs and will include:

- a. Satisfaction with the process of care (on a 5-point scale)
- b. Suggestions for improving the care process (open-ended)

4.6. Statistical analysis plan.

During the survey and visit review components of this study, it became clear that more patients than projected had received pharmacist care. A preliminary analysis conducted on 12/18/2024, prior to evaluating any outcomes, found that the facility assigned to each e-visit usually did \*not\* match the home facility of the patient who initiated the e-visit. This was most likely due to an operational workflow (which is still being elucidated) that was unanticipated at the time this study was designed and facilities were assigned at random to the Pharmacist Care vs. Physician Care groups. Due to the fact that the patient's "home" facility became imbalanced, we will include this as a covariate in the primary analysis (see below).

The primary analysis will group each patient based on which type of clinician (pharmacist or physician) first accessed the eVisit. This is similar to a per-protocol analysis. A patient whose eVisit was first accessed by a pharmacist will be counted in the pharmacist group, even if the eVisit was referred to a physician. A patient whose eVisit was first accessed by a physician will be included in the physician group, even if the eVisit was referred to a physician group, even if the eVisit was referred to a physician group, even if the eVisit was referred to a pharmacist. We select this approach as the primary analysis because it best reflects what patients experience in real-life care delivery, which this study is intended to evaluate.

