A secondary analysis will treat each patient as part of the group to which they were assigned based on the facility listed on the e-visit worklist (intention-to-treat). However, this approach may be worse at reflecting the actual patient experience because dozens of pharmacists and physicians were involved in executing the randomization assignments. It is possible that some patients will have received a different mode of care from the group to which they were assigned.

The primary outcome is binary, i.e., whether or not a patient received counseling for a DDI. This will be compared between study groups using mixed effects logistic regression providing point and interval estimates of outcome odds ratios associated with study group. This analysis technique accounts for the within-facility correlation among patients to obtain valid estimates of treatment effects and associated standard errors. The pre-specified set of covariates for inclusion in regression models include: study group and covariates used in the randomization procedure (i.e. patient socioeconomic status (using the Neighborhood Deprivation Index), patient race/ethnicity, and service area level COVID-19 incidence). Study group and other covariates will be treated as fixed effects and the patient's home facility and e-visit facility will be handled as random effects.

In addition, exploratory/sensitivity analyses will examine the impact of including additional covariates in our estimation of treatment effect, with focus on variables with chance imbalance in distributions by treatment group, as determined in preliminary analyses. Analyses resulting in an appreciable change in the estimate of treatment differences or increased precision of the treatment effect will be noted.

For the secondary outcomes, we will compare the estimated cost per Paxlovid message, the minutes spent per message, and the hours from e-visit to prescription order between the Pharmacist Care and AFM Pool Care groups using linear mixed regression models, providing point and interval estimates of between-group differences in mean outcomes. If cost or minutes have a skewed distribution, log transformation will be used. Analyses of other secondary outcomes with that are continuous will be similar. The approach to inclusion of covariates and sensitivity/exploratory analyses is as described for Aim 1.

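### The primary comparison is by first-accessing clinician type, but the primary model has only facility random effects and no clinician term is named for minutes and cost, so standard errors are too small if outcomes vary between clinicians

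*Combined protocol and SAP*

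**What the plan says.** Section 4.6 (Statistical analysis plan) defines the groups: "The primary analysis will group each patient based on which type of clinician (pharmacist or physician) first accessed the eVisit". Later referral does not move a patient; a patient first seen by a pharmacist "will be counted in the pharmacist group, even if the eVisit was referred to a physician", and the physician group is treated in the same way. In the mixed logistic model for counseling, the patient's "home facility and e-visit facility will be handled as random effects". The plan then relies on this structure: "This analysis technique accounts for the within-facility correlation among patients to obtain valid estimates of treatment effects and associated standard errors". Hours, minutes and cost are to be analysed by linear mixed models. Their random effects are not listed separately, and no clinician term is named.

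Section 4.2 says that in the pharmacist arm "each e-visit message requesting Paxlovid will be assigned to a pharmacist on the regional team". Section 4.5 says that the physicians in a service area cover one another's requests across all its facilities. Section 4.8 plans with a facility ICC of 0.01 and gives no clinician ICC. I found no clinician random effect, clinician-clustered variance or clinician-level sensitivity analysis anywhere in the document.

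**The concern.** The exposure in the primary analysis is a property of the clinician. Every pharmacist's patients are in one group and every physician's patients are in the other, so clinicians are nested in the comparison. Differences between clinicians therefore add directly to the variance of the group contrast. Clinicians also cut across facilities: the pharmacists are one regional team, and physicians cover a whole service area. One clinician's effect is spread over several facility labels, and the facility intercepts cannot stand in for it.

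Variation between clinicians is plausible for these outcomes. Documented counseling is clinician behaviour, minutes are clinician time from access logs, and cost is those minutes times a wage rate. If clinicians vary, confidence intervals are too narrow and the type I error exceeds the planned 5%.

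**Working it through.** **The plan's own figure.** Section 4.8 has 70% counseled with pharmacists, relative risk 0.8 (so 56%), 80% power, two-sided alpha 0.05, facility ICC 0.01 and 250 per group. Two proportions with continuity correction need 200 per group. With 500/17 = 29.4 patients per facility, the design effect is 1 + 28.4 × 0.01 = 1.284, and 200 × 1.284 = 257, within 3% of 250. Without the correction, 186 × 1.284 = 239. The figure is acceptable for facility clustering; clinician clustering is not in it.

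**Inputs for the check.**
- From the documents: 250 per group for the primary outcome; 1,560 e-visits in 17 facilities, about 92 each; facility ICC 0.01; 10 pharmacists, which is the number expected for a survey.
- Assumed: clinician ICC 0.01 to 0.10; 36 physicians; an alternative of 24 pharmacists and 50 physicians; an equal split of the 1,560; equal caseloads within a group.

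**Formula.** In units of the single-patient variance divided by n, the variance with facility clustering only is V0 = 2(1 + f). With clinicians added, V = V0 + ICC(n/k1 − 1) + ICC(n/k2 − 1), where k1 and k2 are the clinician counts. The ratio of true to planned standard error is R = √(V/V0), and the type I error is 2[1 − Φ(1.96/R)].

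**Primary outcome** (n = 250, f = 28.4 × 0.01 = 0.284, V0 = 2.568). Example with ICC 0.05 and 10 and 36 clinicians: V = 2.568 + 0.05 × 24 + 0.05 × 5.94 = 4.065; R = √(4.065/2.568) = 1.258; type I error 11.9%.

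| Clinician ICC | 10 and 36: R | Type I error | 24 and 50: R | Type I error |
|---|---|---|---|---|
| 0.01 | 1.057 | 6.4% | 1.026 | 5.6% |
| 0.02 | 1.111 | 7.8% | 1.051 | 6.2% |
| 0.05 | 1.258 | 11.9% | 1.123 | 8.1% |
| 0.10 | 1.472 | 18.3% | 1.234 | 11.2% |

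**Minutes and cost** (n = 780, f = 91 × 0.01 = 0.91), taking the linear models to carry the same two facility effects:

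| Clinician ICC | 10 and 36 | 24 and 50 |
|---|---|---|
| 0.01 | 8.0% | 6.4% |
| 0.05 | 19.4% | 12.2% |

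Section 4.6 reports more pharmacist care than projected. If pharmacists saw two thirds to three quarters of the 1,560, the figures for 10 and 36 fall to 7.7–7.2% at ICC 0.01 and 18–16% at 0.05.

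**Mitigation.** Suppose the pharmacist ICC is 0.01, the physician ICC is 0.05, and 20% of outcomes are determined by someone other than the first accessor, so that both ICCs are multiplied by 0.8² = 0.64. The primary-outcome rate is then 6.6% (10 and 36) or 5.9% (24 and 50).

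**Simulation, primary outcome.** This used mixed logistic fits with 2,000 replicates per case (Monte Carlo error about 0.5 points), a common rate of 63%, 17 facilities in 4 areas and no patient covariates. With 10 and 36 clinicians the planned model gave 6.2% with no clinician effect, then 6.9%, 8.0%, 12.0% and 17.6% at ICC 0.01, 0.02, 0.05 and 0.10. With 24 and 50 it gave 6.1%, 6.8%, 8.4% and 11.4%. Part of the departure from 5% is therefore not due to clinicians; at ICC 0.01 (10 and 36) their share is 6.9 − 6.2 = 0.7 points.

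A separate simulation with 10 pharmacists and 12 or 40 physicians (600 runs per setting) gave 4.5% or 5.7% without a clinician effect, about 12% at ICC 0.05, and 22% or 17.5% at ICC 0.10.

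**With a clinician intercept added.** Type I error was 5.1–6.3% with a normal reference and 4.4–5.5% with a t reference on clinicians minus 2. The separate simulation (40 physicians) gave 5.3% at ICC 0.05 and 4.8% at 0.10.

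**The case against.** The strongest objection is that the size rests on assumptions. No clinician ICC or front-line physician count is given, and the plan expects small ICCs. Features of the trial may also shrink the effect. Section 4.2 says "Pharmacists will review requests using a standard protocol" and "Drug-drug interactions are documented by pharmacists using a smartphrase in Epic", which may make pharmacists more alike. Referral weakens the tie between first accessor and outcome, and section 4.4.1 counts time from later contacts as well, "including follow-ups that occurred before the initial request was resolved". The 11.9% and 18.3% figures need the same high ICC among protocol-driven pharmacists as among physicians, with no dilution. All of this stands, and it is why the combined case of 5.9–6.6% belongs beside them.

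It is also fair to say that three random intercepts on about 500 patients are demanding: at least one variance was estimated at zero in 81–93% of simulated fits. That is a reason to state how such fits are handled. An unknown ICC is a reason to estimate it, whereas the planned primary model in effect sets it to zero.

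A reader might infer that the trial's type I error is 12% to 18%, or that the primary result is invalid whatever the data show. The documents do not support this. With no variation between clinicians the planned standard errors are about right, and at ICC 0.01 the excess for counseling is small. A reader might also infer that the plan limits the minutes and cost models to facility effects. It does not list their random effects; it only names no clinician term.

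**Conclusion.** The point holds in conditional form. The comparison is by clinician type, clinicians cross facilities, and the plan bases valid standard errors on within-facility correlation alone. If outcomes vary between clinicians, those standard errors are too small.

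The effect is potentially largest for minutes and cost. For the primary outcome it is small at clinician ICC 0.01 and clear at 0.05 and above if pharmacists and physicians vary alike and nothing dilutes the clustering. These sizes depend on assumed ICCs and physician counts and on a survey estimate of 10 pharmacists, so they bound the problem without measuring it. The facility effects remain appropriate and should stay. The change should be made, with medium confidence in how much it matters.

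**What to change.** 1. Add a random intercept for the first-accessing clinician, alongside the two facility intercepts, to the primary, minutes and cost models. State that fits with a variance estimated at zero are kept.
2. In the linear models, test study group with Satterthwaite or Kenward-Roger degrees of freedom. In the logistic model, use a t reference. Clinicians minus 2 performed acceptably in simulation but is not conservative: with 10 and 36 clinicians it gives 44, against a Welch-type value of about 18 to 26, because the 10 pharmacists dominate the variance. Check it by simulation at the actual clinician counts, or use a smaller value driven by the group with fewer clinicians.
3. If the logistic model does not converge, report clinician-clustered standard errors with a small-sample correction as a sensitivity analysis. Note that these ignore facility and may be mildly anti-conservative; a clinician jackknife gave 5.0–6.9% in simulation.
4. Report the number of clinicians and the clinician ICC by group.

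No new data are needed, because the grouping already requires knowing who first accessed each e-visit. The work is a few lines of model code and text, plus a short simulation if clinicians minus 2 is kept. The price is wider intervals if clinicians differ. For the primary outcome the standard error grows by a factor of 1.06 to 1.47 with 10 and 36 clinicians, or 1.03 to 1.23 with 24 and 50, over ICC 0.01 to 0.10. Zero-variance fits will also be frequent.

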#### 4.4.2. Predictors and covariates

The primary predictor is study group, i.e. Pharmacist Care or AFM Pool Care. Covariates are other variables that could potentially mediate, moderate, or confound the association between the primary predictor and the outcomes. In this study, covariates include patient age, sex, race, ethnicity, language spoken, and comorbidities, as well as the patient's neighborhood-level SES.

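### The primary model compares groups defined by who first opened the e-visit, but its pre-specified covariates omit age, sex, language and comorbidities, which the plan itself names as possible confounders

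*Combined protocol and SAP*

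**What the plan says.** Section 4.4.2 sets out what the plan means by a covariate: "Covariates are other variables that could potentially mediate, moderate, or confound the association between the primary predictor and the outcomes". It goes on to say that "covariates include patient age, sex, race, ethnicity, language spoken, and comorbidities", and adds neighbourhood-level socioeconomic status.

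Section 4.6 then defines the groups by care received: "The primary analysis will group each patient based on which type of clinician (pharmacist or physician) first accessed the eVisit". The plan's own description is "This is similar to a per-protocol analysis". The analysis by assigned group is secondary. The change followed the discovery that the facility attached to an e-visit usually differed from the patient's home facility, and the plan explains: "This was most likely due to an operational workflow (which is still being elucidated) that was unanticipated at the time this study was designed".

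For the regression models, section 4.6 states: "The pre-specified set of covariates for inclusion in regression models include: study group and covariates used in the randomization procedure". It spells these out as "patient socioeconomic status (using the Neighborhood Deprivation Index), patient race/ethnicity, and service area level COVID-19 incidence". Home facility and e-visit facility enter as random effects.

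The other variables appear in two further places in section 4.6:
- Sensitivity and exploratory analyses may add covariates. These are not named, and the focus is on variables that turn out to be imbalanced by chance.
- Secondary analyses examine whether the effect varies by age, by race/ethnicity/language group and by comorbidity score group. Sex is not among these.

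The models for cost, minutes and hours to prescription follow the same approach to covariates as the primary outcome, and the satisfaction analyses parallel them.

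**The concern.** Adjusting for the randomisation covariates suits a comparison of randomised groups. In such a comparison the remaining patient characteristics differ only by chance, and the standard error allows for that. The primary contrast is no longer of this kind. Which clinician type opened the request depended on a routing process that the plan says is not yet understood, so nothing in the design guarantees that the two groups have a similar case mix.

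The omitted variables could plausibly bear on the outcome. A patient counts as counselled if any potential interaction was discussed, so a patient with several interacting drugs has more chances to count. Age and comorbidity may track the number of drugs. Both care pathways use telephone calls where needed, so language may also matter. If any of these also differs between the groups, the primary odds ratio mixes case mix with the effect of pharmacist care.

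The plan already accepts the principle: it brings home facility into the primary analysis because it became imbalanced. It does not extend this to the patient characteristics that it lists in section 4.4.2.

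**Working it through.** **1. The plan's own figure.** Section 4.8 gives 250 per group for 70% counselled with pharmacists and a relative risk of 0.8 (0.8 × 70% = 56%), 80% power, two-sided alpha 0.05 and ICC 0.01.
- Two-proportion sample size for 70% vs 56%: 186 per group, or 200 with continuity correction.
- Mean cluster size: 500/17 = 29.4. Design effect: 1 + (29.4 − 1) × 0.01 = 1.284.
- 186 × 1.284 = 239 and 200 × 1.284 = 257. The stated 250 lies between them. Power at 250 per group is 81.9%.

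The sample size therefore reproduces. The design odds ratio is (0.70/0.30)/(0.56/0.44) = 1.83, and ln(1.83) = 0.606.

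**2. Which variables are adjusted for.**

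| Variable in section 4.4.2 | Primary model | Elsewhere in section 4.6 |
|---|---|---|
| Race, ethnicity | fixed effect | effect modifier |
| Neighbourhood SES | fixed effect | – |
| Age | no | effect modifier |
| Language | no | effect modifier |
| Comorbidities | no | effect modifier |
| Sex | no | not named |

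**3. How large the bias could be.** The documents give no imbalance, so these inputs are assumptions. Take one omitted binary factor and no true effect of clinician type. Let x be the probability of counselling without the factor and y the probability with it, where odds(y) = OR × odds(x). With prevalence p in a group, the proportion counselled is x + p(y − x).

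Set A fixes the physician group at 56% counselled with prevalence 40%. For OR 1.5, x = 0.520 and y = 0.619; for OR 2, 0.493 and 0.660; for OR 3, 0.456 and 0.716. Set B fixes x = 56%, so y = 71.8% for OR 2 and 79.2% for OR 3.

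| Set | Factor OR | Prevalence, physician vs pharmacist | Counselled, physician vs pharmacist | Spurious OR | ln(spurious OR)/0.606 |
|---|---|---|---|---|---|
| A | 1.5 | 40% vs 45% | 56.0% vs 56.5% | 1.02 | 3% |
| A | 2 | 40% vs 50% | 56.0% vs 57.7% | 1.07 | 11% |
| A | 3 | 40% vs 60% | 56.0% vs 61.2% | 1.24 | 35% |
| B | 2 | 30% vs 50% | 60.7% vs 63.9% | 1.14 | 22% |
| B | 3 | 30% vs 60% | 63.0% vs 69.9% | 1.37 | 52% |

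Reversing the imbalance reverses the direction.

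In set A the spurious difference is 0.5 to 5.2 percentage points, or 4% to 37% of the 14-point design difference. With an effective 250/1.284 = 195 per group, a nominal 5% test would reject about 5% to 18% of the time. At the upper end, SE = √[(0.56 × 0.44 + 0.612 × 0.388)/195] = 0.050, z = 0.052/0.050 = 1.04, and the rejection probability is 18%.

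**4. Whether the sample can carry the extra terms.** Expected not-counselled patients: 250 × 0.30 + 250 × 0.44 = 75 + 110 = 185. Assume about 7 fixed-effect parameters now (group 1, deprivation index 1, race/ethnicity about 4, incidence 1) and about 6 more: 185/13 = about 14 outcome events per parameter.

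**The case against.** The best defence is that the plan does respond to the one departure it documents, and that these variables are not ignored. Home and e-visit facility are in the primary model, age, language and comorbidity have pre-specified stratified and interaction analyses, sensitivity analyses can add covariates, and the assigned-group analysis gives a second view. Section 4.4.2 also names three possible roles for a covariate and does not say which variable plays which.

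Much of this is true, but none of it adjusts the primary odds ratio. Facility effects deal with clustering and part of the between-facility imbalance, not with differences between patients within a facility. Stratified results may reveal confounding but leave the main estimate as it is. The sensitivity covariates are unnamed, and selecting them for chance imbalance does not fit groups that chance did not form. The assigned-group analysis relies on the worklist facility, which usually differed from the home facility, so its balance is uncertain too. As to roles, all four variables are fixed before the e-visit is opened. They cannot mediate its effect, and adjusting for them removes none of it.

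A reader might infer that older or sicker patients were in fact opened first by one clinician type, and that the primary result is therefore biased. The documents do not support that. They describe assignment of messages by facility and an unexplained workflow, not selection by patient characteristics. Restricting the primary outcome to patients with listed potential interactions may also narrow case-mix differences.

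**Conclusion.** The concern holds as a gap in pre-specification and should be fixed. The primary comparison is of groups not formed by randomisation, its covariate list was built for groups that were, and four variables that the plan lists as potential confounders are left out.

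The size is unknown. Over the assumed range (imbalance of 5 to 30 points, factor odds ratio of 1.5 to 3, one binary factor, no true effect) the spurious odds ratio is about 1.02 to 1.37, against a design odds ratio of 1.83. The low end is negligible and the high end is about half the target on the log scale. The high end needs a 30-point imbalance, for which the documents offer no evidence.

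A reader might also take the model to be adjusted for three variables and nothing else, or take the omitted variables to appear only in analyses chosen after the data are seen. Neither is right: the two facility random effects and the planned effect-modifier analyses are both in section 4.6.

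**What to change.** In section 4.6, add age, sex, language and comorbidity score to the pre-specified fixed effects of the primary model by first-accessing clinician. Do the same in the secondary-outcome models that take the same approach to covariates. Keep the present short-list model as a named sensitivity analysis.

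The change reduces measured confounding only. It does not restore randomisation or deal with unmeasured features of the routing, so the assigned-group analysis should be reported beside the primary result.

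The cost is SAP wording and about six more parameters, at about 14 outcome events per parameter on the assumed count. Availability of the data should be confirmed: the planned effect-modifier analyses imply that age, language and a comorbidity score will be at hand, but sex is named only in section 4.4.2. When the two models are compared, a logistic odds ratio can shift when a prognostic covariate is added even without confounding, so a small difference between them is not by itself evidence of bias.
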